**3. Abstract:**

More Americans suffer from pain than are affected by heart disease, cancer and lung disease. Opioids represent the cornerstone of pain management, yet analgesic responses to opioids are widely variable. Opioid prescriptions have tripled since 1999, paralleled by increases in opioid-related hospitalizations and deaths, contributing to the opioid epidemic. Approximately 35% of all opioid prescriptions originate from surgeons. Hydrocodone, tramadol, and codeine are among the most commonly prescribed opioids, and the cytochrome P450 enzyme, CYP2D6, is central to generation of highly potent metabolites for these opioids. CYP2D6 genotype leads to absent, reduced, normal, or increased function, conferring poor (PM), intermediate (IM), normal (NM) and ultrarapid (UM) metabolism phenotypes, respectively. Data suggest avoiding hydrocodone, tramadol, codeine, and oxycodone in PMs, IMs and UMs because of increased risk for poor response (IM and PM) or toxicity (UM). Leveraging our experience from a recent study, we will test the ***hypotheses that CYP2D6 genotype-guided management of post-surgical pain 1) is feasible, with reduced use of codeine, tramadol, hydrocodone, and oxycodone in PMs/IMs/UMs and 2) will improve post-operative pain control in PMs/IMs***

**and reduce DEA Schedule II (C-II) opioids in NMs.** Patients scheduled to undergo arthroplasty surgery will be recruited from the UF Health Gainesville and the Villages Orthopedic clinics. Patients will be randomized 2:1 to a genotype-guided versus usual care approach. For patients with CYP2D6 PM, IM or UM phenotype based on genotype or drug interactions, a recommendation to avoid hydrocodone, tramadol, codeine, and oxycodone will be made. In others, tramadol will be recommended, given evidence of its lower potential addiction risk than C-II opioids. Patient Reported Outcomes Measurement Information System (PROMIS) measures will be administered at baseline (within 30 days of surgery) and 2 weeks  $\pm$  4 days post-surgery for patients in each arm. Pain scores and assessments of physical functioning, emotional functioning, and mobility from the PROMIS measures and utilization of pain medications during the 2 week period following surgery will be compared between groups.

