## 5. Specific Aims:

The specific aims of our pilot study are to: 1) test the feasibility of a genotype-guided opioid prescribing approach for patients undergoing an outpatient surgical procedure, a group at high risk for persistent opioid use; and 2) evaluate the effect of genotype-guided post-surgical pain management on pain control and opioid prescribing. This will be a randomized, open-labeled pilot pragmatic clinical trial. A total of 320 patients will be recruited from the UF Health Gainesville and the Villages Orthopedic Clinics during their Initial Evaluation for total joint (hip or knee) replacement once the decision for surgery is made. For patients randomized to the genotype-guided arm, a saliva or buccal cell sample will be collected unless venipuncture is done for other reasons and then a blood sample will be collected for genotyping. Genotyping will be performed in the UF Health Pathology Laboratory and results placed in the electronic health record (EHR). For patients in the usual care arm, a genetic sample will be collected for clinical genotyping at the end of the study. At baseline (within 30 days of surgery) and 2 weeks  $\pm$  4 days after surgery, all patients will be asked to complete the PROMIS measures for assessment of pain intensity, physical functioning, emotional functioning, mobility, and a measure of medication misuse. We will also assess utilization of pain medications during the 2 weeks  $\pm$  4 days following surgery. We hypothesize that CYP2D6-guided post-operative pain management is feasible, with reduced use of codeine, tramadol, hydrocodone, and oxycodone in patients with the PM, IM, or UM phenotype, and will improve pain control in PMs and IMs and reduce use of more addictive opioids (i.e. DEA schedule II opioids) in patients with the NM phenotype.

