**Data analysis.** For the primary analysis, we will collect data on the implementation success metrics in **Table 2**. For opioid utilization measures (morphine equivalent dose (MED), schedule IV/II opioid use), we will determine the proportion of patients prescribed specific opioids and self-reported opioid use, since patients may not take any or all of the opioid prescribed. Opioid use (proportion) will be compared between arms by  $\chi^2$  analysis or Fisher's exact test. For our secondary outcome of pain intensity, we will create a composite score of current pain and worst and average pain in last 7 days from the pain intensity subscales. We will use pain intensity at 14 days post-surgery (with a  $\pm 4$  days data capture window). Comparisons between the genotype-guided and usual care groups will be by analysis of covariance (ANOVA), adjusting for baseline pain scores and other baseline differences between the two groups and accounting for MED and/or use of opioids other than tramadol, codeine, hydrocodone, or oxycodone. While beyond the scope of this pilot, we also plan to collect data on prevalence of new persistent opioid use at 6 months (in those who were opioid naive in the year prior to the study) and differences between groups in the PRO of prescription pain medication misuse.

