**Table 2. Clinical Implementation Success metrics**

- % of patients agreeing to participate
- % of patients in genotype arm with a genotype leading to a clinical recommendation for alternative therapy
- % of patients in whom a genetic-guided recommendation is accepted by the clinician
- If recommendation is not accepted, what are the prevailing reasons
- Patient reported opioid use by CYP2D6 phenotype

**Power analysis.** We acknowledge that the proposed trial will have insufficient power to examine PROs (e.g. pain intensity). However, these data will be collected to provide preliminary data on the effects of genotype-guided therapy on PROs to inform a future larger pragmatic clinical trial, and also to document that there are not obvious trends of the genotype-guided approach leading to worse pain control, which in turn could lead to worse post-surgical outcomes. Moreover, if we assume that 25% of patients in the implementation arm will be a PM, IM, or UM (based on genotype and drug interactions) and that codeine, tramadol, hydrocodone, and oxycodone will be avoided in these patients, whereas the remaining 75% of patients in the implementation arm will be prescribed tramadol and nearly all (i.e. 95%) of controls will be prescribed tramadol, codeine, hydrocodone, or oxycodone we will have  $>80\%$  power, with an alpha of 0.05, to detect a difference in use of codeine, tramadol, hydrocodone, or oxycodone between arms.

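### The opioid hypotheses are phenotype-specific, but the only planned opioid test is unstratified and only pooled four-drug use is powered

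*Combined protocol and SAP*

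**What the plan says.** The Specific Aims (section 5) state two opioid hypotheses, each tied to a phenotype: "reduced use of codeine, tramadol, hydrocodone, and oxycodone in patients with the PM, IM, or UM phenotype", and an intention to "reduce use of more addictive opioids (i.e. DEA schedule II opioids) in patients with the NM phenotype". The Abstract (section 3) repeats the second: "reduce DEA Schedule II (C-II) opioids in NMs". Section 6 (Outcomes) makes opioid utilization a primary outcome alongside feasibility.

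The Data analysis paragraph lists morphine equivalent dose and schedule IV/II use as utilization measures. It then gives one opioid test: "Opioid use (proportion) will be compared between arms by" a chi-squared or Fisher's exact test. No phenotype stratum is named.

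The Power analysis paragraph takes 25% of the guided arm to be PM, IM or UM ("based on genotype and drug interactions"). It assumes that "codeine, tramadol, hydrocodone, and oxycodone will be avoided in these patients" and that "the remaining 75% of patients in the implementation arm will be prescribed tramadol". With 95% of controls on one of the four drugs, it claims more than 80% power for a between-arm difference in four-drug use.

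Table 2 lists patient-reported opioid use by phenotype, with no between-arm comparison. It also lists the percentage "of patients in whom a genetic-guided recommendation is accepted by the clinician" as something the pilot will measure.

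**The concern.** Each hypothesis concerns a difference between arms within one phenotype group, and no comparison in the plan is made within such a group. The pooled four-drug endpoint also fits the hypotheses poorly. Section 6 suggests tramadol as first-line opioid for NMs, and tramadol is one of the four drugs. An NM who receives tramadol instead of oxycodone is the change hypothesised for NMs, yet counts as a four-drug user either way. In PM/IM/UM the endpoint does measure the intended change, but averages it with a majority of NMs in whom no fall is expected.

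At stake is what the pilot can report. The Background says that the findings will inform a larger trial, and planning that trial needs each group's between-arm effect and its uncertainty. If clinicians accept only some recommendations, a weak pooled result could sit beside a large PM/IM/UM effect. Stratified comparisons chosen after the data are seen would carry less weight than pre-specified ones.

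**Working it through.** **Inputs.** From the documents: N = 320, randomized 2:1, so about 213 guided and 107 usual care; alpha 0.05; actionable (PM/IM/UM) share 25%; guided four-drug use 0% in PM/IM/UM and 100% in the rest; control use 95%. Assumed: a two-sided test; 95% use in each control phenotype (the plan gives 95% only overall); an acceptance rate *a* (none is given), with unaccepted recommendations leaving use at 95%.

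**Formula.** Two-proportion z-test: power = Φ{[|p1 − p2| − 1.96·√(p̄(1 − p̄)(1/n1 + 1/n2))] / √(p1(1 − p1)/n1 + p2(1 − p2)/n2)}.

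**1. The plan's figure.** Guided rate = 0.25 × 0 + 0.75 × 1.00 = 75%, against 95%. p̄ = (213 × 0.75 + 107 × 0.95)/320 = 0.817. Power = Φ[(0.20 − 1.96 × 0.0458)/0.0364] = 99.9%. Fisher's exact test by enumeration also gives 99.9%. The claim of more than 80% is reproduced.

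**2. Dilution.** PM/IM/UM: 0% against 95%, a fall of 95 points. NM: 100% against 95%, a rise of 5 points. Pooled fall: 0.25 × 95 − 0.75 × 5 = 23.75 − 3.75 = 20 points.

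**3. Incomplete acceptance.** Guided PM/IM/UM use is 0.95(1 − a). Three cases for guided NMs: A, all on tramadol (100%); B, same acceptance as PM/IM/UM; C, unchanged at 95%. At a = 0.5 and 25% actionable, the guided rates are:
- A: 0.75 × 1.00 + 0.25 × 0.475 = 86.9%
- B: 0.75 × 0.975 + 0.25 × 0.475 = 85.0%
- C: 0.75 × 0.95 + 0.25 × 0.475 = 83.1%

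The pooled falls are 8.1, 10.0 and 11.9 points, against 47.5 points within PM/IM/UM.

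Section 4a reports 29% IM/PM after inhibitors and 1% UM, so about 30% actionable. At a = 0.5 the guided rates are then 84.25%, 82.5% and 80.75%.

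| Actionable share | Acceptance (assumed) | Pooled power, A / B / C |
|---|---|---|
| 25% | 70% | 93% / 96% / 99% |
| 25% | 60% | 82% / 90% / 96% |
| 25% | 50% | 63% / 78% / 89% |
| about 30% | 50% | 83% / 92% / 96% |

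**4. Within PM/IM/UM.** 25% of each arm is about 53 against 27. Power at 50%, 40% and 30% acceptance is 99.9%, 98% and 87% at alpha 0.05, and 99.7%, 96% and 78% at 0.025 (the first Holm step for two tests). An observed fall of 47.5 points would have a Newcombe 95% interval of 28 to 61 points. A fall of 28.5 points (30% acceptance) would have 10 to 43.

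**5. Within NM.** 75% of each arm is about 160 against 80. The 95% half-width is at most 1.96 × √(0.25/160 + 0.25/80) = 13.4 points. No control schedule II rate is given; over an assumed 30% to 90%, the fall detectable with 80% power at alpha 0.05 is 15 to 19 points.

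**6. Whole-arm schedule II use.** If NM use fell 20 points and PM/IM/UM use did not change, the whole-arm fall would be 0.75 × 20 = 15 points. At assumed control rates of 30/50/70/90%, whole-arm power is 87/73/74/92%, against 96/86/85/96% in the NM stratum.

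**The case against.** The strongest reply is that this is a pilot and most of what is needed is already planned. Table 2 is part of a primary outcome and includes opioid use by phenotype. Controls are genotyped after follow-up, and prescriptions are collected. The Data analysis wording does not exclude a stratified comparison. A whole-arm test is also a defensible primary comparison, because it needs no phenotype. This stands as far as it goes: the data will exist. But the Table 2 item is patient-reported and has no stated between-arm contrast, so the comparisons that the hypotheses call for are still not pre-specified.

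A reader might infer that the plan cannot show an NM schedule II effect at all. The documents do not support that. Schedule IV/II use is a listed measure, so a whole-arm comparison of it is possible and, on the plan's shares, 75% of its patients are NMs. It is diluted, as step 6 shows. It also does not isolate the NM effect, because PM/IM/UM patients are directed to other drugs, with morphine and hydromorphone among the examples.

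A reader might also infer that the power statement is wrong or the trial underpowered for opioid use. Neither follows. The statement holds at its inputs. The lowest 50%-acceptance figure, 63%, needs every guided NM to receive tramadol while half of the PM/IM/UM recommendations are refused. At about 30% actionable, pooled power exceeds 80% in all three cases. That share comes from a chronic-pain cohort, so how well it transfers is uncertain either way.

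**Conclusion.** The point holds as a mismatch between hypotheses and analysis, and it should be fixed. The pooled four-drug endpoint does not register the NM effect and gives only indirect, diluted evidence on PM/IM/UM: 95 points become 20 on the plan's inputs, if 95% use applies in every control phenotype. Whole-arm schedule II use is informative about NMs but mixed with other phenotypes.

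The loss of power is secondary and conditional. It rests on an acceptance rate that the documents do not give, on what guided NMs receive and on the actionable share. At 50% acceptance the pooled range is 63% to 96% across the cases examined, against about 99.9% within PM/IM/UM at alpha 0.05.

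**What to change.** Keep the whole-arm comparison. Add to the Data analysis paragraph two pre-specified between-arm comparisons, each reported as a difference in proportions with a 95% confidence interval:

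1. In PM/IM/UM: any prescription in the health record of codeine, tramadol, hydrocodone or oxycodone.
2. In NM: any prescription in the health record of a schedule II opioid.

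Assign phenotype by one rule in both arms (genotype plus CYP2D6 inhibitors on the baseline medication list), using the control genotyping already planned. Report missing phenotype by arm. If the two comparisons are to be tested formally rather than estimated, state a fixed order or Holm.

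In the Power analysis paragraph, say that the figure above 80% applies to pooled four-drug use under full avoidance in PM/IM/UM. Add power over a range of acceptance for comparison 1 and the precision for comparison 2 (steps 4 and 5).

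The cost is wording in two paragraphs; no new data or procedures are needed. The drawbacks are small strata of random size and possible missing phenotype in controls who do not complete the 2-week follow-up or whose participation ends because of clinical genotyping. If 20% of control phenotypes were missing (assumed; 53 against 22), power for comparison 1 at 50%, 40% and 30% acceptance would be 99.8%, 96% and 81% at alpha 0.05.

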#### **4a. Preliminary Studies:**

***CYP2D6* genotype-guided pain therapy.** We conducted a pragmatic clinical trial to test the potential clinical benefit of *CYP2D6* genotype to guide tramadol, codeine, oxycodone and hydrocodone in patients with chronic pain (NCT02335307). We enrolled 480 patients with  $\geq 3$  months pain from 9 different primary care clinics at UF Health or the OneFlorida Network. Patients were randomized 2:1 to a genotype-guided intervention or control group (usual care, with genotype reported at study end). NIH-developed and validated Patient Reported Outcomes (PRO) Measures Information System (PROMIS) pain measures were collected from all patients at baseline and 3 months. For the genotype group, genotype data were available approximately 7 days after the baseline clinic visit. Patients were defined as phenotypically *CYP2D6* UMs, NMs, IMs or PMs based on their *CYP2D6* genotype and use of strong or moderate *CYP2D6* inhibitors (according the FDA guidelines). A clinical pharmacist-written consult note was provided on all patients with an actionable (PM, IM, or UM) phenotype. Strong recommendations were made in IMs and PMs against tramadol and codeine, where the impact of *CYP2D6* is clear. Recommendations against oxycodone and hydrocodone were more moderate. Acceptance of the recommended changes was at the physician's discretion. At baseline, median pain intensity based on PROMIS measures was 6.7/10, and 438/480 (91%) were taking an opioid, which included 164 on tramadol, 96 on hydrocodone, 11 on codeine, 125

Protocol #: 201800445

Version Date: 10/02/2019

on oxycodone and 42 on other opioids. Based on genotype, 1% were UM, 11% were IMs or PMs, and when considering phenoconversion by strong or moderate CYP2D6 inhibitors, 29% were IMs or PMs. Patients treated with tramadol, hydrocodone or codeine at baseline had improvements in the genotype-guided arm in pain intensity. In the group for whom the benefit was expected (IMs and PMs), analyses revealed significantly greater improvements for genotype-guided versus usual care for numerous pain intensity subscales (Figure 1). A clinically meaningful 30% reduction in pain score was observed in 24% of genotype guided versus 0% of usual care patients ( $p=0.04$ ). There was also a significant reduction in pain intensity when also considering hydrocodone use at baseline ( $p=0.02$ ).

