For patients in the genotype arm, *CYP2D6* genotyping will be done in the CAP/CLIA-licensed UF Health Pathology Laboratory at Rocky Point with results reported in the EHR. It is expected that results will be reported prior to surgery in the absence of any genotyping error. Patients will be categorized as *CYP2D6* PM, IM, NM, or UM based on *CYP2D6* genotype/activity score and FDA guidance on drug interactions. Strong inhibitors (e.g. bupropion, fluoxetine, paroxetine) phenoconvert patients to PMs, with moderate inhibitors (e.g. duloxetine, fluvoxamine) reducing *CYP2D6* activity scores by 50%. Using a standardized consult note, as we are using for an on-going study in cancer pain patients (NCT02664350), recommendations will be made to avoid tramadol, hydrocodone, codeine, and oxycodone in PMs, IMs, and UMs and to use an alternative opioid (e.g. morphine, hydromorphone) or non-opioid (e.g. NSAID). Consideration of tramadol as the first line opioid will be recommended for NMs. Patients randomized to usual care will have their DNA sample collected at the Initial Evaluation visit and stored until they have completed the 2 week follow-up, at which time, the sample will be genotyped with the result reported in the EHR. This approach was successfully used in our previous study in chronic pain. Genotyping will be funded by the grant. Patients will be compensated in the amount of \$25 gift certificate for their participation. Study participation will be terminated for any patient

randomized into the usual care arm who gets genotyping done for clinical care before study completion. These patients will receive \$10 compensation for study participation.

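### The pain hypothesis concerns poor and intermediate metabolizers, but the only planned pain analysis compares whole arms and adjusts for post-operative opioid use; prespecify PM/IM and NM contrasts with baseline covariates only

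*Combined protocol and SAP*

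**What the plan says.** The hypothesis is specific to phenotype. The Abstract says that genotype-guided management "will improve post-operative pain control in PMs/IMs", and Specific Aims says that it "will improve pain control in PMs and IMs and reduce use of more addictive opioids", the second clause referring to normal metabolizers (NMs). Preliminary Studies reports the earlier chronic-pain trial in the same terms: "In the group for whom the benefit was expected (IMs and PMs").

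The analysis is not specific to phenotype. Under Data analysis in the Research Plan, the pain composite at 14 days is handled in one sentence: "Comparisons between the genotype-guided and usual care groups will be by analysis of covariance (ANOVA"). The covariates are baseline pain, unnamed baseline differences, and a further item: "accounting for MED and/or use of opioids other than tramadol, codeine, hydrocodone, or oxycodone". MED is morphine equivalent dose, which the same paragraph lists among the opioid utilization measures. Opioid utilization is a primary outcome under Outcomes. No subgroup, stratum or interaction is mentioned.

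The only outcome listed by phenotype is in Table 2: "Patient reported opioid use by CYP2D6 phenotype". The Power analysis paragraph concedes insufficient power for patient-reported outcomes. It says that those data should inform a larger trial and "document that there are not obvious trends of the genotype-guided approach leading to worse pain control".

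**The concern.** There are two linked problems.

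First, the hypothesis and the estimate refer to different populations. An analyst who follows the plan to the letter produces no PM/IM pain estimate. A null whole-arm result would say little about the hypothesis, because most patients in it are not expected to benefit. If the PM/IM estimate is produced later anyway, its phenotype definition, covariates and time point will have been chosen with the data in view. The larger trial would then rest on weaker evidence.

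Second, the extra covariates arise after randomisation and are what the intervention acts on. The Research Plan states that "recommendations will be made to avoid tramadol, hydrocodone, codeine, and oxycodone in PMs, IMs, and UMs and to use an alternative opioid". Conditioning on the resulting opioid choice or dose takes out of the arm coefficient whatever works through that choice. It can also bias what remains, in either direction, where dose and pain share causes. As written, the whole-arm model does not estimate the total effect of the strategy, and a PM/IM model that copied its covariates would inherit the fault.

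**Working it through.** **Inputs from the document.** N = 320 (Research Plan), randomised 2:1 (Abstract), so 213.3 guided v 106.7 usual care. The Power analysis assumes 25% PM, IM or UM (ultrarapid metabolizer). Preliminary Studies gives 1% UM, 11% PM/IM by genotype alone and 29% PM/IM once inhibitor drugs are counted. Background gives PM 5–10% and IM 2–11%, which sum to 7–21%. The PM/IM shares examined are therefore 29%, 24% (25% less 1% UM), 21% and 11%.

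**Assumptions.** The document gives no pain SD, effect size or dropout rate. Results are in residual SD units, with two-sided alpha 0.05, a normal approximation, the same phenotype share in both arms and, unless stated, no dropout.

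**The plan's own figure.** The only power statement (>80%) concerns use of the four opioids, 75% v 95%. With 213 v 107:
- pooled proportion 0.817, null SE 0.0458, alternative SE 0.0364
- (0.20 − 1.96 × 0.0458)/0.0364 = 3.03, giving 99.9% power

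The statement is correct, but it does not cover pain.

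**Precision of a PM/IM contrast.** SE = √(1/n₁ + 1/n₂), half-width = 1.96 × SE, 80% detectable difference = 2.80 × SE.

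| PM/IM share | Guided v usual care | SE | 95% half-width | 80% detectable |
|---|---|---|---|---|
| 29% | 61.9 v 30.9 | 0.220 | 0.43 | 0.62 |
| 24% | 51.2 v 25.6 | 0.242 | 0.47 | 0.68 |
| 21% | 44.8 v 22.4 | 0.259 | 0.51 | 0.72 |
| 11% | 23.5 v 11.7 | 0.358 | 0.70 | 1.00 |

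With an assumed 15% non-response, the half-width and detectable difference become 0.51 and 0.74 SD at 24%, and 0.76 and 1.09 SD at 11%.

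**Dilution in the whole-arm comparison.** Its SE is √(1/213.3 + 1/106.7) = 0.119 and its half-width 0.23. If only PMs and IMs benefit, whole-arm effect = share × PM/IM effect. For an assumed 0.5 SD PM/IM benefit:

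| Share | Dilution (1/share) | Whole-arm effect | Power, whole-arm | Power, PM/IM |
|---|---|---|---|---|
| 29% | 3.4 | 0.145 | 23% | 62% |
| 24% | 4.2 | 0.120 | 17% | 54% |
| 11% | 9.1 | 0.055 | 7% | 29% |

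At 24%, a worsening of 0.24 × 0.5/0.75 = 0.16 SD in NMs would cancel the 0.5 SD PM/IM gain entirely.

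**NM contrast.** At 75% NM (160 v 80) the half-width is 1.96 × √(1/160 + 1/80) = 0.27 SD. It ranges from 0.25 to 0.28 SD as the NM share runs from 88% to 70%. Power for a 0.16 SD worsening is about 22%.

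**Copying the opioid adjustment into a PM/IM model (illustration).** Suppose guided PMs and IMs avoid the four drugs with probability *a*, controls with probability 0.05, and avoiders take another opioid. With 2:1 weights, r² = (2/9)(*a* − 0.05)² / [m(1 − m)], where m = (2/3)*a* + (1/3)(0.05). SE inflation is 1/√(1 − r²), with residual SD held fixed.
- *a* = 1.0 (the Power analysis assumption): m = 0.683, r² = 0.93, inflation 3.7. The half-width at 24% goes from 0.47 to 1.75 SD.
- *a* = 0.75: r² = 0.44, half-width 0.63 SD.
- *a* = 0.5: r² = 0.20, half-width 0.53 SD.

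For the whole-arm model actually planned (25% v 5% avoiding), r² = 0.059 and inflation is 1.03, so the half-width goes from 0.232 to 0.240 SD. The objection to adjustment there concerns what is being estimated, not precision.

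**The case against.** The strongest reply is that the whole-arm comparison is the right one. Aim 2 in Specific Aims asks about the effect of guided management on pain without limiting it to a phenotype, and the check for worse pain control concerns the approach as a whole. That stands: the whole-arm comparison should be kept. It does not supply the estimate that the hypothesis in the same section calls for.

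Second, the plan already calls the pain data preliminary and underpowered, and a PM/IM interval of ±0.43 to ±0.70 SD would guide a larger trial only weakly. This is true. It is a reason to report an interval and make no claim, and it limits the severity of the point. It is not a reason to omit the relevant estimate.

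Third, the NM hypothesis concerns schedule II opioids, not pain. The NM pain contrast is therefore a safety check only. It bounds the size of any harm but would often miss a small one.

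Fourth, several figures are extremes. The 11% share ignores the drug interactions that the plan counts in its phenotype definition. The 3.7-fold inflation assumes full avoidance and no switch to non-opioids, which the recommendations allow, and applies only to a PM/IM model that copies the adjustment. Both are bounds and should be read that way.

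Fifth, usual-care patients are genotyped only after the 2-week follow-up, and those genotyped clinically before completion leave the study. Phenotype could therefore be missing unequally by arm. The phenotype rule needs to deal with this, but most controls who are never genotyped will also lack day-14 pain.

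**Conclusion.** The concern holds. No section supplies a PM/IM pain estimate, and the one planned pain model conditions on consequences of the intervention. It therefore neither answers the pain part of the hypothesis nor estimates the total effect of the strategy.

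If benefit is confined to PMs and IMs, the whole-arm comparison shrinks it about 3.4- to 4.2-fold at shares of 29% to 24%, and up to 9.1-fold if phenoconversion by inhibitor drugs were absent. The share in this trial is uncertain: the 29% came from chronic-pain patients, 91% of them on an opioid, whereas this trial excludes chronic opioid therapy.

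Because pain is secondary and the trial is a pilot, this is an inexpensive improvement that should be made. It is not a threat to the primary outcomes.

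**What to change.** In the Data analysis paragraph:

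1. Keep the whole-arm day-14 comparison. Adjust it for baseline pain and a fixed, named list of baseline covariates, without MED or post-operative opioid choice.
2. Add a prespecified day-14 model with arm, phenotype (PM/IM v NM) and their interaction, using the same baseline covariates.
3. Report the PM/IM contrast with its 95% CI as the preliminary estimate for the pain part of the hypothesis, and the NM contrast with its 95% CI as a check for worse pain. Make no significance claim, and do not make either contrast conditional on the interaction p-value, whose own half-width would be about 0.55 SD at 24%.
4. Describe UMs only. At 1–2% of 320 there would be about 3–6 in total and 1–2 in usual care.
5. Label any MED- or opioid-adjusted model, including the whole-arm one, as supplementary.
6. Define phenotype identically in both arms, from genotype plus CYP2D6-inhibitor use at one time point fixed in advance, before surgery and before any consult note. The date of randomisation would serve, since both arms have one. Report how many patients in each arm have no phenotype.

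The cost is analysis text and one derivation rule. DNA is collected from everyone, usual-care samples are genotyped after the 2-week follow-up, and chronic and pre-operative medications are already recorded. The document gives no capture date for those medications, so the rule must fix one. The downside is limited PM/IM precision, which the intervals will show.
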